6.2. Study Drug Administration

CCH is a sterile lyophilized powder that is reconstituted with a sterile diluent made of 0.6% sodium chloride and 0.03% calcium chloride dihydrate in water. Subjects who qualify for the study will be given a maximum total dose of approximately 0.21 mg CCH over the course of the study, which will be administered as 3 doses of 0.07 mg CCH each, approximately, during 2 or 3 dosing sessions. Refer to the study schema in Section 1.2 for the dosing sessions. There are 2 treatment areas. Group 1, Group 2, and Group 3 will have 2 dosings with the single injection technique in Treatment Area 1 and 1 dosing with the single injection technique in Treatment Area 2 at specified study visits. Group 4, Group 5, and Group 6 will have 2 dosings with the [REDACTED] in Treatment Area 1 and 1 dosing with the [REDACTED] in Treatment Area 2 at specified study visits. The maximum study dose per treatment area is approximately 0.14 mg CCH and the minimum dose per treatment area is approximately 0.07 mg CCH. See [Table 1](#) for details.

At each dosing visit, the CCH injection dose administered per treatment area (Area 1 or Area 2) in Group 1, Group 2, and Group 3 is 0.07 mg CCH/0.3 mL administered subcutaneously as [REDACTED] of [REDACTED] mL with a single injection technique, or in Group 4, Group 5, and Group 6 is approximately 0.07 mg CCH/1.5 mL administered subcutaneously as [REDACTED] of [REDACTED] mL with a [REDACTED] (see [Table 1](#)).

Specific instructions for CCH reconstitution and administration, including the injection techniques, will be provided in the Pharmacy Manual. Study treatment will be injected subcutaneously while the subject is in a supine position. Specific instructions outlining the injection techniques will be provided in the Clinical Operations Manual.

Table 1: Study Treatment (All Subjects)

Group	Injection Technique	Dose per Each Administration	Volume per Each Dose	Number of Doses	Dose (mg) at Each Treatment Area	Cumulative Study Dose
1, 2, 3	Single injection	CCH 0.07 mg	0.3 mL (given as three [REDACTED] mL aliquots)	2 doses in Treatment Area 1 and 1 dose in Treatment Area 2	0.14 mg in Treatment Area 1 and 0.07 mg in Treatment Area 2	0.21 mg
4, 5, 6	[REDACTED]	CCH 0.0653 mg	1.4 mL ^a (given as [REDACTED])	2 doses in Treatment Area 1 and 1 dose in Treatment Area 2	0.13 mg in Treatment Area 1 and 0.0653 mg in Treatment Area 2	0.196 mg

^a [REDACTED] mL of the 1.5 mL dilution will be remaining and returned to Endo as described in Section 6.3.

NOTE: CCH is a foreign protein and investigators must be prepared to address and manage an allergic reaction should it occur. At the time of each injection, a 1:1,000 solution of epinephrine for injection, 50-mg diphenhydramine injection or a suitable equivalent, and oxygen must be available with the investigator and site staff must be familiar with their use. To evaluate the subject for possible immediate immunological AEs, the subject will remain in direct observation of medical personnel who are skilled in the management of an allergic reaction for 30 minutes after receiving the injections of study treatment and until the subject exhibits no sign of an immunological or other clinically significant systemic or local AE. The subject's vital signs must be stable before the subject can leave direct observation.

The investigator or qualified designee will then apply a sterile dressing to the injection areas with hypoallergenic tape. The subject will be instructed to remove the dressing in the evening.

6.3. Study Treatment Preparation/Handling/Storage/Accountability

CCH and its diluent will be supplied in bulk. Each vial of study treatment and diluent will minimally be labeled with contents, sponsor identification, storage, administration/use, and appropriate caution statements. CCH and the diluent must be stored in an appropriate, secure area. Study treatment must be kept in a temperature-monitored refrigerator (2°C to 8°C) with locked access until used or returned to Endo or designee.

The investigator or designee will confirm that appropriate temperature control conditions have been maintained for all study treatments received and any discrepancies are reported per instructions in the Pharmacy Manual and resolved prior to study treatment administration.

Only subjects enrolled in the study will receive study treatment and only authorized trained study staff will dispense and administer study treatment.

Any remaining unused reconstituted study drug will be stored and returned to Endo or designee.

In accordance with the International Council for Harmonisation (ICH) requirements, at all times the investigator will be able to account for all study treatment furnished to the study site. An accountability record will be maintained for this purpose. The investigator must maintain accurate records indicating dates and quantity of study treatment received, to whom it was administered (subject-by-subject accounting) and accounts of any study treatment accidentally or

deliberately destroyed. All unused study treatment not involved in immediate subject treatment will be maintained under locked, temperature-controlled storage at the study site.

Please refer to the Pharmacy Manual for complete information regarding preparation of study treatment and administration syringes, as well as, handling, storage, and accountability of study treatment.

6.4. Measures to Minimize Bias

This is an open label, nonrandomized study. The pathologist, who is blinded to the dosing schedule, will report any observed tissue differences from the control area (not injected).

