3. Histopathology and immunohistochemistry of the excised abdominal tissue.

Following a screening period of up to 28 days, subjects will be assigned to 1 of 6 groups. Each subject will have 2 marked areas (Area 1 and Area 2) of the abdomen dosed with CCH (single or multiple doses) plus a marked non-dosed control area for comparison. The control area will be located between the 2 treatment areas. By the end of the dosing phase, Treatment Area 1 will receive a total of 2 doses (referred to as multiple doses in the objectives) at specified study visits for the group assigned, and Treatment Area 2 will receive a total of 1 dose (referred to as single dose in the objectives) at specified study visits for the group assigned. Refer to the study schema in Section 1.2 for additional details.

Disclosure Statement: This is an open-label exploratory study with 6 dosing arms. The pathologist reporting the results will be blinded to the dosing schedule.

Number of Subjects (planned):

It was originally planned that 8 subjects (1 or 2 subjects per group) enroll and complete the study. Due to COVID-19 restrictions and impacts, an additional 2 subjects will be enrolled to replace (for overall objective and endpoint analysis purposes) subjects whose abdominoplasty surgeries were delayed due to COVID-19 restrictions. The 2 subjects whose surgeries were delayed due to COVID-19 are still planned to complete the study. While the safety data of these subjects will be considered for safety analysis, the histopathology data of their abdominoplasty tissue specimens would be analyzed separately.

Treatment Groups and Duration:

Subjects in each group will receive up to 3 CCH doses (each dose as either a [REDACTED] single injection technique or a [REDACTED]) across 2 treatment areas at the following dosing visits:

Group 1 and Group 4 (n = 2 subjects/group): Dosing on Days -43 and -22, and -14.

Group 2 and Group 5 (n = 1 subject/group): Dosing on Days -24 and -3.

Group 3 and Group 6 (n = 1 subject/group): Dosing on Days -22 and -1.

[figure not shown]
At each dosing visit, the CCH injection dose administered per treatment area (Area 1 or Area 2) is approximately 0.07 mg CCH/0.3 mL (administered subcutaneously as [REDACTED] of [REDACTED] mL each in a single injection technique in Group 1, Group 2, and Group 3) or approximately 0.07 mg CCH/1.5 mL (administered subcutaneously as [REDACTED] of approximately [REDACTED] mL each in a [REDACTED]

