- i All photographs should be taken after marking the treatment and control areas with a surgical marker, but prior to CCH injection or abdominoplasty surgery. No manipulation of the treatment or control areas should be done prior to the photographs being taken.
- j Treatment Area 1 in Group 1 and Group 4 will receive the first treatment on Day -22 (Note: for Group 1 and Group 4, treatment on Day -14 will occur in Treatment Area 2 NOT in Treatment Area 1). (Please see **Study Schema Section 1.2**).
- k Local AEs associated with the injection site, including acute (eg, erythema, bruising, pain, nodules/mass, ulceration, blistering, pruritus, swelling, and/or induration) and/or chronic (eg, skin thickening, fibrosclerosis, and peau d'orange changes) cutaneous AEs, will be recorded and evaluated for seriousness and severity.
- l Day 0 samples for anti-AUX-I, anti-AUX-II, and neutralizing antibodies may be collected as part of the standard of care presurgical visit that is nearest to the scheduled date of the abdominoplasty procedure (after dosing visits are completed).

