6.1. Selecting and Marking Treatment Area

Each subject will have 2 marked areas (Area 1 and Area 2) of the abdomen selected for injection with CCH plus a marked non-injected control area for comparison (Figure 2). The control area will be located between the two treatment areas. Treatment areas of each subject group will be marked: Treatment Area 1 and Treatment Area 2 with the noninjected area marked as Control.

At each dosing visit, the treatment areas of each selected subject will be photographed **after marking the treatment area and the injection site with a surgical marker and a temporary tattoo (but prior to CCH dosing or the abdominoplasty procedure)**, while the subject is in a consistent, standardized relaxed standing pose. On Day of Surgery (Day 0), prior to abdominoplasty procedure, the borders of the treatment area will be marked with a surgical

marker. Following marking, the treatment areas will then be photographed while the subject is in a standing pose (as previously described). Additional instructions will be provided in the Clinical Operations Manual.

Figure 2: Diagram of Treatment Areas

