8.1.7. Gross Pathology, Histopathology, and Immunohistochemistry

Digital photography will be conducted so that the photographs of the treatment area can assist the histopathologist/evaluator in assessing the gross pathology and histopathology of the excised tissues. Refer to the Clinical Operations Manual for the length of time of tissue storage.

At each dosing visit, the treatment areas of each selected subject will be photographed after marking the treatment area and the injection site with a surgical marker (but prior to CCH injection), while the subject is in a consistent, standardized relaxed standing pose.

At Day 0 (Day of Surgery), the treatment areas will be again photographed after marking the treatment area but prior to the abdominoplasty procedure, while the subject is in a consistent, standardized relaxed standing pose.

No manipulation of the treatment or control areas should be done prior to the photographs being taken.

The marked and photographed abdominal tissue that is isolated and excised during the abdominoplasty procedure will be shipped to a pathology laboratory for analysis according to instructions in the Clinical Operations Manual. All tissue samples will be handled by the pathologist according to instructions in the Histopathology Manual.

Histopathology and immunohistochemistry of the excised abdominal tissue will be performed at the central pathology laboratory. The pathologist, who is blinded to the dosing schedule, will report any observed tissue differences from the control area (not injected).

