9.3.1. Histopathology and Immunohistochemistry

Histopathology and immunohistochemistry findings in the excised abdominal tissues injected with CCH will be compared to histopathology and immunohistochemistry findings in non-injected control tissue. Also, histopathology and immunohistochemistry findings in the excised abdominal tissues dosed twice with CCH will be compared to histopathology and immunohistochemistry findings in excised abdominal tissues dosed only once with CCH.

The pathologist, blind to the dosing schedule, will report any observed tissue differences from the control area (not injected).

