3.6. Blinding and Randomization

This is an open label, non-randomized study. The pathologist, who is blinded to the dosing schedule will report any observed tissue differences from the control area (not injected).

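### The only masking stated is to the dosing schedule, which as written does not protect the primary comparison of dosed tissue with control tissue

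*Protocol*

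**What the plan says.** The study is open-label and nonrandomized. Masking of the pathologist is described in five places, each time in the same limited terms:

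- Protocol 1.1 (Synopsis): "The pathologist reporting the results will be blinded to the dosing schedule".
- Protocol 6.4: "The pathologist, who is blinded to the dosing schedule, will report any observed tissue differences from the control area (not injected").
- Protocol 8.1.7 repeats the sentence in 6.4.
- Protocol 9.3.1: "The pathologist, blind to the dosing schedule, will report any observed tissue differences from the control area (not injected").
- SAP 3.6: "The pathologist, who is blinded to the dosing schedule will report any observed tissue differences from the control area (not injected").

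The primary endpoint (Protocol section 3) is the change in histopathology and immunohistochemistry of dosed tissue relative to tissue that was not dosed, for each treated area and each injection technique.

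On marking, section 6.1 has the areas labelled "Treatment Area 1 and Treatment Area 2 with the noninjected area marked as Control", with the control placed between the two treated areas in every subject. Footnote i of the Schedule of Activities says "All photographs should be taken after marking the treatment and control areas with a surgical marker". Section 8.1.7 gives the purpose of the pictures, that "photographs of the treatment area can assist the histopathologist/evaluator in assessing the gross pathology and histopathology"; SAP 3.7 says the same. Section 8.1.7 also has the marked tissue shipped to the laboratory and adds: "All tissue samples will be handled by the pathologist according to instructions in the Histopathology Manual".

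**The concern.** Masking to the dosing schedule hides when, and perhaps how often, an area was injected. It does not hide whether the area was injected at all, and that is the primary contrast. Section 6.4 is the section on minimizing bias, and this is the only masking it offers.

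The endpoint is what a pathologist reports seeing. The protocol and SAP give no scoring scale, no second reader and no hypothesis test (Protocol 9.3, SAP section 6). Results are reported in subject narratives. A reader who knows which piece is the control may report differences more readily in the injected pieces. With no test or scale to fall back on, masked reading is the main protection available for this comparison.

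**Working it through.** The plan states no figure for this point, so the check compares texts and then counts the readings affected.

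**1. What is masked against what is compared**

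| Item | Source | Content |
|---|---|---|
| Masked | Protocol 1.1, 6.4, 8.1.7, 9.3.1; SAP 3.6 | Dosing schedule |
| Primary contrast | Protocol 3 | Dosed versus non-dosed tissue |
| Reading task | Protocol 6.4, 8.1.7, 9.3.1; SAP 3.6 | Differences from the non-injected area |

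The masked item and the compared item differ. Read plainly, the task also assumes that the reader can tell which area is the control.

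**2. Routes by which control identity could reach the reader**

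- The skin is labelled by name, including the control (6.1).
- The control is in the middle in every subject (6.1), so position alone identifies it on an oriented specimen.
- Photographs follow the marking of treatment and control areas (1.3, footnote i) and are meant to help with histopathology as well as gross pathology (8.1.7; SAP 3.7).
- Marked tissue is shipped, and the pathologist handles the samples (8.1.7).

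**3. Steps that would block these routes**

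Neither document mentions coded specimens, masking of area identity or a random reading order. Section 8.1.7 refers to the Histopathology Manual and the Clinical Operations Manual, which were not supplied.

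**4. Number of readings concerned**

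- Planned subjects by group (Protocol 4.1): 2 + 1 + 1 + 2 + 1 + 1 = 8. This matches the 8 completers in Protocol 9.1 and SAP 3.5. Adding the 2 delayed-surgery subjects gives 10.
- Primary comparisons per finding: 8 subjects x 2 treated areas = 16, read against 8 controls. Masking of the control is stated for none of the 16.
- Tissue already excised at Amendment 4: 6 subjects had had surgery (Protocol 2.1), so 6 x 2 = 12, and 12/16 = 75%. This counts tissue excised, not slides read; the number of slides read is not given.
- Area specimens to code: 8 x 3 = 24, or 10 x 3 = 30 with the delayed-surgery subjects. Slides per area are not given.

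**5. A related exposure**

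Area 1 always receives two doses and Area 2 one (Protocol 1.2). A reader who saw the area labels and knew the design could infer the number of doses, so the secondary Area 1 versus Area 2 comparison could be open in the same way.

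**The case against.** The strongest reply is that the protocol and SAP are only silent. Slide labelling, coding and reading order would plausibly be set out in the manuals. Photographs taken on the skin before surgery need not be open while slides are scored, and handling samples does not mean that slides carry area labels. Differences from control can also be derived after a coded reading. The term for what is masked is undefined and could be stretched to cover dosing by area, although the reference to the non-injected area in the same sentence weakens that reading.

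This stands as far as it goes. A reader might infer that the pathologist scores with the control known, or that the primary findings are biased. The documents do not support either inference: neither says that control identity is disclosed at scoring, and neither gives any basis for a size of bias.

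A second reply is that the study is exploratory, has one or two subjects per group and tests nothing, so little depends on it. That limits the consequence but does not remove the gap, because the unprotected comparison is the primary endpoint.

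A third is that coding may not fully mask. Groups 2, 3, 5 and 6, which are 1 + 1 + 1 + 1 = 4 of the 8 planned subjects, are dosed on Day -3 or Day -1, and Protocol 2.3 names bruising as the most common injection site reaction. Recently injected tissue may identify itself. This is an inference, but a fair one, and it counts as a limit on the remedy.

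**Conclusion.** The point holds for what the protocol and SAP state. Their masking covers the dosing schedule and not control identity, so as written it does not protect any of the 16 dosed-versus-control comparisons per finding. This should be fixed, because it concerns the primary endpoint and the remedy is cheap.

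The conclusion is limited to the written plan. It does not establish that any slide was or will be read unmasked, and it would reduce to a missing cross-reference if the manuals already require coded reading. No decision rule or error rate depends on the result. What is at stake is the reliance that can be placed on the descriptive findings. The counts assume that the main histopathology analysis rests on the 8 subjects in Protocol 9.1 and SAP 3.5, with the 2 delayed-surgery subjects analysed separately.

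**What to change.** Amend Protocol 6.4, 8.1.7 and 9.3.1 and SAP 3.6 and 3.7 to state that:

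1. Photographs and area labels are used for gross mapping and block selection.
2. Laboratory staff then code each subject's three areas (Area 1, Area 2, Control) in random order within subject. Coding within subject keeps the paired comparison that the plan specifies; pooling slides across subjects would lose it.
3. The same pathologist records microscopic and immunohistochemistry findings on the coded set and locks them. Only then are the codes opened and differences from control derived.

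If the manuals already require this, a sentence in 6.4 saying so is enough. For slides already read, report which readings were masked; those read unmasked could be masked only by a coded re-read.

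Costs and limits: a coding step for at least 24 area specimens (30 with the delayed-surgery subjects), no photographs during scoring, and wording changes in both documents. No extra reader is needed. Masking would be only partial if the same pathologist did the gross mapping, which is likely given that the pathologist handles all samples, or if recent injection leaves visible bruising.

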6.5. Study Treatment Compliance

All subjects will receive study treatment administered by the investigator at the study site. All dosing information will be recorded for each subject visit. Drug inventory will be maintained in an accountability record at the study site, and all original containers of used and unused study treatment and diluent will be returned to the sponsor (or designee) at the end of the study.

Accidental or intentional overdoses should be reported to the sponsor/designee promptly (see Section 8.3).

6.6. Prior and Concomitant Medications and Procedures

The investigators will provide the sponsor with a listing of the standard of care medications routinely given to subjects undergoing pre-planned, elective abdominoplasty surgery. These standard medications, when used prophylactically (such as antibiotics), and as part of routine surgical administration (such as oxygen supplementation, standard intravenous fluids, medications used in anesthesia, and blood products), are not required to be recorded via the electronic case report form (eCRF)/electronic data capture (EDC) system. In the event that any of these medications cause or are used to treat an AE that occurs during presurgery preparation, or during surgery or postsurgery, the corresponding AE and the medication will be recorded.

For all other medications, the start and stop date, dose, unit(s), frequency, route of administration, and indication for all prior (taken within the 90 days prior to the Screening Visit) and concomitant (taken from the Screening Visit through the Day 28 End of Study/Early Termination Visit) medications will be recorded. Nondrug therapies (eg, blood transfusions, physical therapy, and occupational therapy) received will also be recorded.

6.6.1. Prohibited Medications and Procedures

The following medications are prohibited for subjects during the study: anticoagulants (warfarin, heparin, direct thrombin inhibitors, Factor X inhibitors) and antiplatelet agents (aspirin > 150 mg/day and P2Y12 inhibitors, such as clopidogrel), which can cause additional bruising. However the use of aspirin at a dose level of \leq 150 mg per day will be permitted during the study.

The following procedures are not allowed in the abdominal area during the course of the study (from the Screening Visit through Day 0):

- Injections (eg, mesotherapy), radiofrequency device treatments, laser treatment, cryolipolysis, or surgery (including subcision and/or powered subcision).
- Any investigational treatment in the abdominal area.
- CoolSculpting® or similar treatments of the abdomen during the 18-month period before injection of study drug.
- Deep massage therapy (such as Endermologie™) or similar therapy, within the abdominal area.
- Creams (eg, Celluvera™, TriLastin®) and/or home therapies within the abdominal area.
- Bath/shower salts or sugar/salt scrubs, lotions, loofahs, or other exfoliating products on the abdominal area.

If any prohibited medication or procedure is used during the study, all pertinent information will be recorded. The designated study medical monitor must be informed immediately so the sponsor may determine whether to continue the subject in the study.

